3.5.7 Sample Size and Power Calculations

3.5.7.1 Sample Size and Power for Immunogenicity Analyses

This study will include approximately 1,200 women into each of the 2 age groups (27- to 45-year-old subjects and 16- to 26-year-old subjects).

The power of the study was calculated using SAS Version 9.3 based on the assumption of log-normality of the post-vaccination titres.

The analysis of the immunogenicity endpoints will follow a Per Protocol approach. In the scope of the study, i.e., an immunogenicity study with a 3-dose HPV vaccination schedule on women 16- to 45-years of age, the rate of dropout and general protocol deviations deemed as having potential to interfere with evaluation of immune response to GARDASIL®9 leading to exclusion from the per protocol analysis is expected to be less than 15%. Based on a previous study conducted with GARDASIL® in 24- to 45-year-old women (Study V501 Protocol 019), it is assumed that 10 to 20% of enrolled subjects would be seropositive at baseline for a given HPV type. This would lead to an overall rate of exclusion from the PPI analysis populations ranging from 25% to 35% of enrolled subjects. Given these exclusion rates, starting with 1,200 enrolled subjects (600 per age group), [Table 8](#) shows the number of evaluable subjects and the corresponding power for one single comparison depending on the percentage of subjects excluded from the PPI analysis populations.

Table 8 Study Power Depending on Exclusion Rates

Number of enrolled subjects per group	Estimated percentage of subjects excluded from the PPI Sets	Number of evaluable subjects per group	Standard deviation (natural log scale)	Expected GMT ratio AW/YAW	Power for one single comparison
600	35%	390	1.2	0.7	0.97
600	25%	450	1.2	0.7	0.99

AW, adult women; GMT, geometric mean titre; PPI, per protocol immunogenicity; YAW, young adult women.

The expected GMT ratio AW/YAW is 0.7, reflecting the fact that the immunogenicity of any HPV vaccines decreases with the increasing age of the subjects. It is to be noted that the study may result in an upper bound of the two-sided 95% CI around the GMT ratio AW/YAW being lower than 1, although the non-inferiority would be demonstrated if the lower bound is greater than 0.5 (i.e., the non-inferiority margin). If 1,200 subjects are enrolled in the study in a 1:1 fashion with regards to the 2 age groups, the evaluable population will range from 780 to 900 subjects. If the exclusion rate from the Per Protocol analysis is 35% for 1 HPV type and 25% for the 6 others, this study will have over 90% power to rule out a 2-fold decrease in GMT for the 7 oncogenic HPV types (Types 16, 18, 31, 33, 45, 52, and 58). The power calculation is based on an estimate of 1.2 for the variability of each serotype on the natural log scale and assumes that the true GMT ratio AW/YAW is 0.7 which is based on the results from Study V501 Protocol 019 where GMTs were observed to decrease with age at vaccination.

Assuming a true seroconversion rate to each HPV type >98% and a percentage of subjects excluded from the PPI analysis populations <35% for HPV 16 and <25% for HPV 18, 31, 33, 45, 52, and 58, the power of the secondary hypothesis testing is >99% using Type I error $\alpha=0.025$ (one-sided).

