1.4 Summary of Study Design

This study will enrol a total of approximately 1,200 subjects, i.e., 600 women 16- to 26-years-old and 600 women 27- to 45-years-old, all of whom have not yet received a prophylactic HPV

³ Muñoz N, Manalastas R Jr, Pitisuttithum P, Tresukosol D, Monsonego J, Ault K, et al. Safety, immunogenicity, and efficacy of quadrivalent human papillomavirus (types 6, 11, 16, 18) recombinant vaccine in women aged 24–45 years: a randomised, double-blind trial. Lancet. 2009 Jun 6;373:1949-57.

⁴ Castellsagué X, Muñoz N, Pitisuttithum P, Ferris D, Monsonego J, Ault K, et al. End-of-study safety, immunogenicity, and efficacy of quadrivalent HPV (types 6, 11, 16, 18) recombinant vaccine in adult women 24–45 years of age. Br J Cancer. 2011;105(1):28-37.

⁵ Luna J, Plata M, Gonzalez M, Correa A, Maldonado I, Nossa C, et al. Long-term follow-up observation of the safety, immunogenicity, and effectiveness of Gardasil™ in adult women. PLoS ONE. 2013;8(12):e83431.

⁶ Joura EA, Garland SM, Paavonen J, Ferris DG, Perez G, Ault KA, et al. Effect of the human papillomavirus (HPV) quadrivalent vaccine in a subgroup of women with cervical and vulvar disease: retrospective pooled analysis of trial data. BMJ. 2012 Mar 27;344:e1401.

⁷ Kang WD, Choi HS, Kim SM. Is vaccination with quadrivalent HPV vaccine after loop electrosurgical excision procedure effective in preventing recurrence in patients with high-grade cervical intraepithelial neoplasia (CIN2-3)? Gynecol Oncol. 2013 Aug;130(2):264-8.

vaccine. The study will provide a comparison of immunogenicity of GARDASIL®9 in 27- to 45-year-old women, with 16- to 26-year-old women, with respect to the 7 oncogenic HPV types (Types 16, 18, 31, 33, 45, 52, and 58). The responses to the two non-oncogenic HPV types included in the vaccine (Types 6 and 11) will be presented using descriptive statistics. The number of subjects to be enrolled in the study was determined based on the primary immunogenicity objective.

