2.4 Study Design and Duration

2.4.1 Summary of Study Design

This is an international, multicentre; open-label, immunogenicity and tolerability study of GARDASIL®9 in 16- to 45-year-old women.

Approximately 1,200 healthy women, all of whom have not yet received a prophylactic HPV vaccine, will be enrolled in the study (i.e., 600 YAW between 16 to 26 years of age and 600 AW between 27 to 45 years of age). Each age group will be divided in 2 strata defined as 16- to 20-year-olds and 21- to 26-year-olds for YAW and 27- to 36-year-olds and 37- to 45-year-olds for AW. The immunogenicity data will be summarized by strata and age group, and the safety data will be summarized for 16- to 26-year-old women and 27- to 45-year-old women. All enrolled subjects will receive a 3-dose regimen (Day 1, Month 2, and Month 6) of GARDASIL®9. Serum samples will be obtained on Day 1 and Month 7 for anti-HPV 6, 11, 16, 18, 31, 33, 45, 52, and 58 testing. Immunogenicity analyses will be performed after all subjects have completed the Month 7 visit.

Medical history (past year) will be collected on Day 1 for all subjects. Oral temperature will be measured prior to each vaccination. Vital signs (height, weight, and oral temperature) will be collected on Day 1. Physical examination will be conducted on Day 1 if deemed necessary by the investigator.

Subjects will be monitored for safety and tolerability from Day 1 through 1 month following the third vaccination or for a total of approximately 7 months for each subject. A pregnancy test will be performed before administration of each dose of the study vaccine and at the final Month 7 visit on all subjects. The pregnancy test must be performed prior to serum collection for HPV testing at Day 1. Any subject with a positive pregnancy test at Day 1 will not be vaccinated and will not be allowed to participate in the study. Subjects with a positive pregnancy test after Day 1 will not be vaccinated with subsequent doses until resolution of the pregnancy as outlined in **Table 3**. Pregnant subjects who receive less than 3 vaccinations during the study will be offered the possibility to complete the vaccination course. Pregnancies and associated adverse experiences will be followed to outcome.

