The choice of the non-inferiority margin is driven by the clinical relevance and the expected variability of the endpoints, and the desired accuracy of the conclusions of the study. A 2-fold non-inferiority margin is considered as appropriate to assess any negative trend in immunogenicity with GARDASIL®9 in 27-45 year-olds women compared with 16-26 year-olds women. Specifically, it is reflecting the fact that the immunogenicity of any HVP vaccines decreases with the increasing age of the subjects making impossible the use of a more stringent non-inferior margin (e.g., 1.5). In addition a more stringent margin is considered to be of limited interest as there is currently no known minimum immunologic correlate for HPV vaccine efficacy, due to high efficacy of the vaccine; such margin would not be expected to add further clinical significance to the results.

This study will include approximately 1,200 women into each of the 2 age groups (27- to 45-year-old subjects and 16- to 26-year-old subjects). Each age group will be further stratified into subgroups of 16- to 20-year-olds and 21- to 26-year-olds for YAW and 27- to 36-year-olds and 37- to 45-year-olds for AW. Enrolment will be monitored to make sure that no single age

stratum (i.e., subgroup) exceeds 55% of the total sample of a given age group (i.e., enrolment in an age stratum will be stopped when around 330 subjects in that age stratum have been vaccinated).

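### Sections 3.1.2.2 and 3.5.7.1 state 1,200 women per age group, twice the 600 per group behind the power table, stratum cap and safety table

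*Combined protocol and SAP*

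**What the plan says.** Two sections of the current text set the enrolment target at 1,200 per age group:

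- Section 3.5.7.1, opening sentence: "This study will include approximately 1,200 women into each of the 2 age groups".
- Section 3.1.2.2, last paragraph: "This study will include approximately 1,200 women into each of the 2 age groups (27- to 45-year-old subjects and 16- to 26-year-old subjects".

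Elsewhere the target is 1,200 in total:

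- Section 1.4: "a total of approximately 1,200 subjects, i.e., 600 women 16- to 26-years-old and 600 women 27- to 45-years-old".
- Section 2.4.1: "600 YAW between 16 to 26 years of age and 600 AW between 27 to 45 years of age".
- Section 2.4.2: about 1,200 women receive the 3-dose regimen.
- Section 3.5.7.1, third paragraph: "starting with 1,200 enrolled subjects (600 per age group". Both rows of Table 8 list 600 enrolled per group.
- Sections 2.7.1 and 3.5.7.1: 1,200 women enrolled 1:1 leave 780 to 900 evaluable.
- Section 3.5.7.1.1 and Table 9: the safety probabilities assume 1,200 vaccinated women.

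The enrolment control in sections 1.5 and 3.1.2.2 also bears on the point. No single "stratum (i.e., subgroup) exceeds 55% of the total sample of a given age group", and the text converts this to a count: "enrolment in an age stratum will be stopped when around 330 subjects in that age stratum have been vaccinated".

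**The concern.** The plan states two enrolment targets that differ by a factor of 2, and one of them opens the section that justifies the sample size. The sentence is complete and has the same wording in both places, so damaged text does not explain it, and it is not in the summary of changes. As worded, it can only mean 2,400 women.

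The larger figure also conflicts with its surroundings. In 3.5.7.1 it contradicts Table 8. In 3.1.2.2 it stands in the same paragraph as a stratum stop that would close each age group well short of it.

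A coincidence makes misreading easier. Excluding 25% to 35% of 1,200 leaves 780 to 900, and the plan gives those numbers as the evaluable total over both groups. A reader who starts from the opening sentence could take them as per-group numbers. If the sentence were copied into a study report or publication, a trial that enrolled its intended 1,200 would appear to have reached half its target.

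**Working it through.** **Inputs, all from the plan.** Expected GMT ratio 0.7 and SD 1.2 on the natural log scale (Table 8); non-inferiority margin 0.50 and one-sided alpha 0.025 per type (2.7.1, 3.5.5.1); exclusion from the PPI populations 25% to 35% (3.5.7.1); stratum cap 55%, about 330 women, with two strata per age group (1.5, 3.1.2.2).

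**Step 1: reproduce Table 8 at 600 per group.** The difference on the log scale is ln(0.7) − ln(0.5) = 0.3365. Evaluable women per group are 600 × 0.65 = 390 and 600 × 0.75 = 450. With n evaluable per group, power is approximately Φ(0.3365 / (1.2 × √(2/n)) − 1.96).

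- n = 390: 0.3365 / 0.0859 = 3.915; 3.915 − 1.96 = 1.955; power 0.9747 (noncentral t: 0.9745). Table 8 states 0.97.
- n = 450: 0.3365 / 0.0800 = 4.206; 4.206 − 1.96 = 2.246; power 0.9876 (noncentral t: 0.9875). Table 8 states 0.99.

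Overall power, with one type at 35% exclusion and six at 25%, is 0.9745 × 0.9875⁶ = 0.904 if the seven tests are independent. The plan states over 90%. Independence is assumed here; the plan does not say how it obtained its figure.

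**Step 2: compare the two readings.**

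| Quantity | Plan states | 600 per group (1,200 total) | 1,200 per group (2,400 total) |
|---|---|---|---|
| Evaluable per group, 35% / 25% excluded | 390 / 450 | 390 / 450 | 780 / 900 |
| Evaluable in total | 780 to 900 | 780 to 900 | 1,560 to 1,800 |
| Power, one type | 0.97 / 0.99 | 0.975 / 0.988 | 0.9998 / 0.99997 |
| Power, seven types (independent) | over 0.90 | 0.904 | 0.9996 |
| 55% stratum cap | about 330 | 0.55 × 600 = 330 | 0.55 × 1,200 = 660 |
| At least one event, true rate 0.1% | 70% | 69.9% | 90.9% |
| At least one event, true rate 0.05% | 45% | 45.1% | 69.9% |
| At least one event, true rate 0.01% | 11% | 11.3% | 21.3% |
| 99% upper bound with no events | < 0.39% | 0.38% | 0.19% |

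The event probabilities are 1 − (1 − p)^N and the bound is 1 − 0.01^(1/N), with N the total vaccinated.

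**Step 3: can 1,200 per group be reached?** Each age group has two strata. If each closes at about 330, the group closes at about 2 × 330 = 660, which is 55% of 1,200. A cap of 330 in a group of 1,200 would be 330 / 1,200 = 27.5%, not 55%.

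**What does not discriminate.** The claim of more than 99% power for the seroconversion hypotheses does not help to choose. At a true rate of 98% that power already exceeds 0.999 with 390 women, so it would hold under either reading.

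**The case against.** The best defence is that nobody who reads the whole section could be misled. Two paragraphs after the wrong sentence, 3.5.7.1 gives 600 per age group, and both rows of Table 8 repeat it. The likeliest explanation is that the words for each group slipped into a sentence meant to describe both groups together. Type I error, margin, analysis populations, model and decision rule are untouched, and all the power figures are right for 600 per group. Enrolment to 2,400 could not happen in practice, because the stratum stop limits each group to about 660. The power above 0.999 describes a trial that nobody intends to run.

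All of this stands as a statement about consequences. The error is one of wording: it introduces no bias, loses no power and puts no participant at risk. It does not follow that the sentence can stay. The stratum stop limits the damage only because it contradicts the sentence, and the number at fault is the one this section exists to state. A reader should not have to work out the target by setting one paragraph against another.

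**Conclusion.** The contradiction is real and the intended figure is not in doubt: 1,200 women in total, 600 per age group. Sections 3.1.2.2 and 3.5.7.1 overstate the target by a factor of 2 (2,400 against 1,200). The stated power, the stratum cap and the safety table are consistent with 600 per group and need no change. This rests on the plan's own inputs (ratio 0.7, SD 1.2, margin 0.50, one-sided 0.025, 25% to 35% excluded). Independence between HPV types is needed only for the overall figure of 0.904, and the conclusion does not depend on it. The practical effect is small, but a wrong enrolment target at the head of the sample size section should be corrected.

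**What to change.** In both 3.1.2.2 and 3.5.7.1, replace the sentence with, for example: *Approximately 1,200 women will be enrolled in total, about 600 per age group.* This agrees with sections 1.4, 2.4.1 and 2.4.2, Tables 8 and 9, and the stop at about 330 per stratum. While editing, say next to the 780 to 900 range that it is the total over both age groups (390 to 450 per group), so that it cannot be read as a per-group figure.

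The cost is one sentence in each of two sections, plus the optional clarification. No recalculation is needed, and enrolment and study procedures do not change.

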3.5.7.1.1 Sample Size and Power for Safety Analyses

The probability of observing at least 1 vaccine-related SAE in this study depends on the number of subjects vaccinated and the underlying incidence rate in the study population. [Table 9](#) shows the probability of observing at least one vaccine-related SAE within the 1,200 subjects who will receive GARDASIL®9 for various theoretical incidence rates.

Table 9 Probability of Observing At Least One Vaccine Related Serious Adverse Event for Various Theoretical Incidence Rates

Incidence Rates	Probability of at Least 1 Serious Adverse Event
1.0%	99%
0.5%	99%
0.1%	70%
0.05%	45%
0.01%	11%

If no vaccine related SAE is observed in the 1,200 subjects who will receive GARDASIL®9 in this study, there is a 99% probability that the true incidence rate is <0.39%.

3.5.8 Interim Analysis

No interim analysis is planned.

3.6 DEFINITION OF COMPLIANCE MEASURE

Compliance is defined in this study as receipt of all scheduled study vaccinations. To summarise compliance, the numbers of subjects who receive each vaccination will be tabulated. Compliance with the planned vaccination schedule (Day 1, Month 2, and Month 6) will be described by histograms of actual intervals between vaccinations relative to the expected interval in the CSR.

3.7 Labeling, Packaging, Storage, Dispensing, and Return of Clinical Supplies

3.7.1 Product Description

Investigational Medicinal Product (IMP) will be provided by the Sponsor as summarized in [Table 10](#).

Table 10 Investigational Medicinal Product

Product Name	Potency	Dosage Form/ Contents/Route of Administration	Storage Conditions
GARDASIL®9 V503 (9-Valent HPV L1 VLP) Vaccine (Recombinant, adsorbed)	HPV Types (L1 protein) 6/11/16/18/31/33/45/52/58 30/40/60/40/20/20/20/20/20 mcg Adsorbed on AAHS 500 mcg	Sterile suspension for intramuscular injection 1 dose (0.5 mL) Shake well before use.	Store at 2.0 to 8.0°C (35.6°F and 46.4°F). Do not freeze. Protect from light.
AAHS, Merck Aluminum Adjuvant (amorphous aluminum hydroxyphosphate sulfate); HPV, human papillomavirus; VLP, virus-like particle.			

GARDASIL®9 is available as a suspension for injection. It appears as a clear liquid with white precipitate.

3.7.2 Packaging Information

Supplies will be labelled in accordance with local regulatory requirements.

3.7.3 Clinical Supplies Disclosure

Not applicable. This study is open-label.

3.7.4 Shipment of Investigational Medicinal Product

The IMP will be shipped to the study sites, refrigerated and stored at 2.0°C to 8.0°C (35.6°F to 46.4°F). Upon receipt at the study site, the vaccine should be removed from the outer secondary shipping box and placed immediately into the refrigerator.

Each shipment will include an electronic temperature-monitoring device to verify maintenance of the cold chain during transport, as well as an Acknowledgement of Receipt form.

Upon arrival of the shipment at the study site, the person responsible will verify that the content of the shipment corresponds to the order and that the products arrived in good condition. He/she will acknowledge receipt in IRT. For temperature excursions noted via the device, the temperature data recorded during shipment will be downloaded. The current customer complaint process should be followed to acknowledge the excursions.

3.7.5 Storage and Handling Requirements

For details on storage and handling requirements, please see Section 3.7.5.. The storage conditions will be indicated on the product label.

The clinical supplies storage area at the study site must be monitored by the site staff for temperature consistency with the acceptable storage temperature range specified in this protocol or in the product label attached to the protocol. Documentation of temperature monitoring should be maintained. Supplies should be stored in the original nested box with the lid closed to minimize exposure to light. If the refrigerator in which the study vaccine is stored deviates from the 2.0°C to 8.0°C range (35.6°F to 46.4°F), study vaccinations should be suspended and the Sponsor (or designee) should be contacted immediately. Vaccine must NOT be frozen.

A daily refrigerator temperature log must be maintained at the study site. The refrigerator must be equipped with an appropriately calibrated min/max thermometer and/or circular chart temperature recorder. The temperature log will be reviewed by the Clinical Research Associate (CRA) throughout the study. An appropriate back up system (i.e., alarm or generator) and study site personnel telephone numbers should be in place in the event of a refrigerator failure.

In case of a cold chain break (i.e., if the temperature of the refrigerator is lower than 2.0°C or exceeds 8.0°C [lower than 35.6°F or exceeds 46.4°F]):

The investigator (or designee) at the site should follow the current clinical complaint process to file an excursion

The investigator (or designee) must wait for further instructions from the Sponsor or from the CRA, as to whether or not the study vaccines can be used. The investigator is not allowed to use the study vaccines before getting the Sponsor (or designee) approval to do so.

The cold chain break must be documented in the Investigator Site File and in the Trial Master File.

The IMP must be received by a designated person at the study site, handled and stored safely and properly, and kept in a secured location to which only the investigator and designated assistants have access. IMP is to be administered only in accordance with the protocol.

Any concerns raised about the manufacturing, packaging, labelling, or distribution of IMP supply which could potentially impact its suitability for use should be immediately reported to the Sponsor. The IMP must be quarantined until the Sponsor feed-back is received as to whether or not the vaccine can be used.

Unused study vaccines taken out from the stock at study site are considered to be unusable and cannot be returned to the stock. They must be quarantined and returned back to the Sponsor (or designee) as soon as possible.

3.7.6 Accountability of Investigational Medicinal Product

For the accountability procedure, please refer to Guidelines for IMP Management on site.

3.7.7 Return of Investigational Medicinal Product

All empty primary containers will be destroyed at the study site according to local regulations. Supplies will need to be returned to the depot of origin if destruction is not possible locally.

Empty boxes of study vaccines must be kept at study site to enable verification of the vaccine accountability by the CRA (or designee) and can afterwards be destroyed on site.

The following should be returned to the distributor according to the procedures detailed in the Investigator Site File:

Study vaccines unusable following a cold chain deviation, as soon as possible;

Study vaccines expiring within the current month, immediately;

Unused study vaccines which remain in stock at study site after the last administration to the last subject of the corresponding study site, after verification of vaccine accountability;

Study vaccines concerned by a batch recall, immediately.

The CRA (or designee) will organise the return of unusable and unused study vaccines, which should be returned by ambient transport. The list of the returned study vaccines should be enclosed in the returned package. For the return procedure, please refer to Guidelines for IMP Management on site. The distributor will confirm the receipt of each study vaccine returned (at unit level).

